## 3. Concise Summary of Project:

This trial will be a comparative pragmatic open label randomized controlled trial of daily versus alternate day dosing of oral iron in anemic pregnant patients.

Two randomly assigned groups will be compared during the antepartum period:

- 1. Control Group: standard of care, daily oral iron supplementation (325 mg PO daily ferrous sulfate)
- 2. Intervention Group: alternate day dosing oral iron supplementation (650 mg PO every other day ferrous sulfate)

325mg Ferrous sulfate is a standard oral iron supplement providing 65 mg of elemental iron per dose. Standard dosing recommendations for the treatment of iron deficiency anemia is between 65 to 200 mg elemental iron daily.

Each group will receive a phone survey 2-4 weeks after initiation of therapy to assess side effects of each group as well as compliance. Call is anticipated to last approximately 10-15 minutes. This survey has previously been validated in assessing gastrointestinal symptoms for those taking oral iron supplementation (33).

The number of subjects studied will be 86 subjects at UTMB, we plan to approach and consent up to 96 patients to allow for screening failures, early withdrawals, and patients lost to follow-up, and patients who must withdraw due to failure of therapy. Failure of therapy for the purposes of this study will be patients who require parental iron supplementation or transfusion. Study to last an anticipated length of 3 years. If our sample size is not achieved, we will submit to the IRB an addendum to increase the number of consented subjects to achieve the desired sample size.

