### Secondary outcomes:

- Assessment of GI adverse effects determined by survey
- Analysis of CBC indices including reticulocyte count, MCV, etc.
- Iron studies at time of diagnosis
- Need for parental iron supplementation
- Need for transfusion in the peripartum period
- Postpartum hemoglobin and hematocrit
- Neonatal weight
- Presence of antepartum fetal growth restriction
- Neonatal outcomes such as NICU admission, hyperbilirubinemia, and APGAR scores
- Relationship of obesity to effectiveness of supplementation in both study arms

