#### Screening

All pregnant patients undergo a laboratory screen for anemia at the first prenatal appointment as part of the UTMB standard of care. Eligible patients (1st or 2nd trimester patients with a hemoglobin below 11 g/dl or 10.5 g/dl respectively) will be screened and approached at their next prenatal appointment for consent (detailed under section 9). We request a waiver to screen these patients.

The anticipated procedures flow is as follows

- 1. Research staff will travel to location
- 2. Research staff will confirm with provider that possible subjects are appropriate candidates for treatment with ferrous sulfate
- 3. Research staff will approach screened patients to obtain consent from possible subjects
- 4. Subjects will be randomized using a randomization log with group assignment, subject name, and medical record number
  - a. Daily dosing group will take ferrous sulfate 325 mg (65 mg elemental iron) by mouth daily
  - b. Alternate day dosing group will take ferrous sulfate 650 mg (130 mg elemental iron) by mouth every other day
- 5. Prescriptions for the appropriate regimen will be provided by the research staff
  - a. If the research staff is a physician, the appropriate prescription will be sent at time of encounter
  - b. If the research staff is a non-physician, a physician research staff member will be alerted and the appropriate prescription will be sent on the same day
- 6. After patient is consented and enrolled, the provider will be notified and a note will be placed in the electronic chart indicating that the patient is enrolled in the study.

- 7. Subjects will continue to receive standard, routine prenatal care and surveillance of iron deficiency anemia in pregnancy
  - a. Research staff and PI will monitor surveillance data by chart review
- 8. 2-4 weeks after initiation of respective iron regimen research staff will contact subjects by phone to administer a 5-10 min survey to assess GI side effects and compliance with regimen.
- 9. Research staff will conduct chart review to obtain the datapoints for the primary and secondary outcomes (described in section 1)

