### Survey Details

2-4 weeks after randomization, the patient will receive a phone call from a member of research staff to conduct a brief 5-10 min survey to assess gastrointestinal side effects of iron supplementation and compliance. Patients will be made aware of this survey in the consenting process. Study subjects will then resume standard prenatal care visits.

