## 13. Potential Benefits:

The potential benefits of the study to the intervention group (alternate day dosing) include:

- 1. Improved fractional absorption of iron with corresponding improvement of anemia compared to standard oral iron replacement therapy
- 2. Decreased GI side effects with alternate day dosing

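### GI side effects are taken from one call at 2-4 weeks with no stated recall period and no record of GI-related stopping, so a woman who stopped iron for GI upset and recovered may be scored as unaffected

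*Combined protocol and SAP*

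**What the plan says.** GI tolerability is a listed secondary outcome: "Assessment of GI adverse effects determined by survey". Section 3 gives the timing: "Each group will receive a phone survey 2-4 weeks after initiation of therapy to assess side effects of each group as well as compliance". The procedure list in Section 4 (under Screening) has research staff phone the subject "to administer a 5-10 min survey to assess GI side effects and compliance with regimen".

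Survey Details, also in Section 4, counts the interval from a different starting point, "2-4 weeks after randomization, the patient will receive a phone call from a member of research staff", and ends the contact with "Study subjects will then resume standard prenatal care visits". No baseline, repeat or end-of-treatment GI survey is described.

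On the instrument, Section 3 says: "This survey has previously been validated in assessing gastrointestinal symptoms for those taking oral iron supplementation". Its items, recall window and scoring are not reproduced.

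Section 14 gives generic tests: t or rank-sum for continuous variables, chi-square or Fisher for categorical ones, and a relative risk with 95% CI for dichotomous endpoints. It does not mention the survey, compliance, or how to score a woman who is no longer taking iron.

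Section 13 lists two potential benefits of the intervention; the second is "Decreased GI side effects with alternate day dosing".

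**The concern.** Stopping treatment is itself an expression of intolerance, and a symptom score taken once, some weeks into therapy, can miss it. A woman who gives up iron in the first week because of nausea or constipation may have nothing left to report at week 3. If the score reflects only recent symptoms, one of the clearest cases of intolerance is counted as none.

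The compliance questions might show that she stopped, but nothing in the documents says that the reason is asked or that the answer enters the GI comparison. No later contact is planned at which it could be recovered.

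At stake is the tolerability conclusion. Section 2 cites lower GI side effects as part of the rationale for alternate-day dosing, and Section 13 makes it one of two claimed benefits. The regimens are expected to differ in tolerability, so they may also differ in how many women stop because of it. The survey result could then not be read cleanly in either direction.

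**Working it through.** **No GI figure to reproduce.** The documents state no GI event rate, effect size, power or stopping rate. The sample size in Section 14 rests on hemoglobin. All GI rates below are therefore assumptions and serve only to show scale.

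**Inputs**
- n = 39 per arm, the superiority figure in Section 14.
- Two-sided 5% significance level (Section 14); chi-square test, computed as the pooled z test.
- p = true proportion of women ever affected by GI symptoms before the call (assumed).
- s = share of affected women who stopped or reduced iron, recovered, and score as unaffected (assumed).

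**Model.** Observed rate = p × (1 − s). The chance of a significant result comes from exact enumeration of two binomials with n = 39.

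**A. No true difference: p = 40% in both arms.** Either arm may be the one with the larger s.

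| s, one arm | s, other arm | Observed rates | Significant, chi-square | Significant, Fisher |
|---|---|---|---|---|
| 0% | 0% | 40% vs 40% | 5.1% | 3% |
| 0% | 10% | 40% vs 0.40 × 0.90 = 36% | 6.6% | 4% |
| 10% | 30% | 0.40 × 0.90 = 36% vs 0.40 × 0.70 = 28% | 12% | 7% |
| 10% | 50% | 36% vs 0.40 × 0.50 = 20% | 36% | 27% |
| 0% | 50% | 40% vs 20% | 50% | 39% |

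With a 10-point gap in s the error rate barely moves. It becomes serious only when the gap is large.

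**B. A true benefit of alternate-day dosing: p = 40% daily, 20% alternate-day.** The true relative risk is 0.20 / 0.40 = 0.50 and the true difference is 20 points.

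| s daily | s alternate-day | Observed daily vs alternate-day | Relative risk | Difference |
|---|---|---|---|---|
| 20% | 20% | 32% vs 16% | 0.50 | 16 points |
| 20% | 10% | 32% vs 18% | 0.56 | 14 points |
| 30% | 10% | 28% vs 18% | 0.64 | 10 points |
| 50% | 10% | 20% vs 18% | 0.90 | 2 points |
| 60% | 10% | 16% vs 18% | 1.12 | −2 points |

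Three things follow.
1. Recovered stoppers lower the observed rate in whichever arm they belong to.
2. On the planned relative-risk scale, an equal share in both arms causes no distortion, although the absolute difference still shrinks.
3. If the share is larger in the daily arm, the relative risk moves toward 1, and past it in the extreme case.

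**Dosing and non-dosing days.** The call is not tied to the dosing day. Under a short recall period, some alternate-day women would be asked about a day without iron, which could lower their reported symptoms. Others would be asked about a day on which they took 130 mg elemental iron, against 65 mg in the daily arm, which could raise them. The net direction cannot be determined from the documents.

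**The case against.** The strongest objection is that the mechanism depends on a questionnaire that is not in the documents. If it asks about any symptom since starting iron, a recovered woman still counts as affected and the main bias disappears. This stands. What the documents show is that the recall period and the handling of women who stopped are unstated; they do not show that a bias exists.

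A second objection is that compliance is asked in the same call, so women who stopped may be identifiable and could be tabulated. This stands in part. Section 14 specifies no such analysis, and compliance alone does not separate stopping for nausea from stopping for any other reason.

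Third, the larger figures in table A need gaps of 20 to 50 points in stopping, for which the documents give no support. A 10-point gap gives 6.6% against 5.1%. This stands, and it limits how much weight the illustration can carry.

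Fourth, altering a validated questionnaire, or replacing its score with a composite that includes stopping, has its own cost. Self-attributed reasons for stopping in an open-label trial are open to reporting bias. This also stands, and argues for adding items alongside the survey score rather than redefining it.

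A reader might infer that the design inflates the benefit claimed for alternate-day dosing, or that off days can only favour that arm. The documents support neither. Sections 2 and 13 expect daily dosing to be worse tolerated, in which case lost stoppers work against the study's own hypothesis. The doubled single dose leaves the dosing-day effect without a known sign.

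**Conclusion.** The point holds as a gap in how a secondary outcome is defined and collected. GI side effects rest on one call at 2-4 weeks. No recall period is stated, the documents do not provide for recording the reason for stopping, and compliance does not enter the GI analysis. If recall is short, women who stopped for GI upset and recovered can be missed. The relative risk is then distorted to the extent that their share differs between arms.

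The size is unknown. Under an assumed 40% true rate in both arms, it ranges from negligible (about 7% significant results with a 10-point gap) to large (about 50% with a 50-point gap). Under the protocol's own expectation, the likelier consequence is that part of a real tolerability advantage of alternate-day dosing is hidden. The documents do not support the stronger statement that severe intolerance is scored as none, because no scoring is given.

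The primary hemoglobin result is unaffected. The change is worth making because it is cheap and because the information is not planned to be collected anywhere else.

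**What to change.** 1. Keep the validated questionnaire and its score as the GI outcome, and state its recall period and scoring in the protocol.
2. Add two items to the same call: whether iron was stopped, skipped or reduced because of GI symptoms at any time since starting, and whether any GI symptom has occurred since the first dose, on dosing or non-dosing days.
3. In Section 14, report the proportion who stopped or reduced iron for GI reasons by arm, beside the survey result. Add a supplementary analysis that counts those women as affected.
4. Reconcile the starting point of the 2-4 week window, which is initiation of therapy in Section 3 and in the procedure list, but randomization in Survey Details.

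The cost is one or two extra questions in a call that already covers compliance, with no added visit, blood draw or change in sample size. The added items are not part of the validated instrument, and self-attributed reasons may be influenced by knowledge of the assigned regimen. They should therefore supplement the survey score and not replace it.

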#### 4. Study Procedures:

#### Patient Population

The patient population will be selected from obstetric patients receiving prenatal care in the UTMB health system. This population can broadly be divided into patients cared for by one of the UTMB faculty obstetric providers and those who receive care through the Regional Maternal and Child Health Program (RMCHP). We anticipate that the majority of the patients in this study will be recruited from the RMCHP patients.

#### Locations

All RMCHP clinics locations will be possible recruitment sites, however we anticipate that the bulk of the recruitment will occurs at the Galveston, Pasadena, and Angleton clinics were the PI and perinatal research division staff are frequently located. Research staff will travel to each clinic and consenting and enrolling will only occur when research staff are present.

#### Research Team

The research team (or research staff) will consist of the PI, faculty sponsor, trained research coordinator, and additional staff to be trained and added to the research protocol. All members of the research team will be able to screen and consent subjects. Physician research team members will be responsible for providing the prescriptions to patients who agree to take part in this study. The PI and faculty sponsor will work together to ensure that the team is of sufficient size to carry out the project. Consenting and enrollment of subjects will only occur when a research team member is physically present at a study location.

#### Screening

All pregnant patients undergo a laboratory screen for anemia at the first prenatal appointment as part of the UTMB standard of care. Eligible patients (1st or 2nd trimester patients with a hemoglobin below 11 g/dl or 10.5 g/dl respectively) will be screened and approached at their next prenatal appointment for consent (detailed under section 9). We request a waiver to screen these patients.

The anticipated procedures flow is as follows

- 1. Research staff will travel to location
- 2. Research staff will confirm with provider that possible subjects are appropriate candidates for treatment with ferrous sulfate
- 3. Research staff will approach screened patients to obtain consent from possible subjects
- 4. Subjects will be randomized using a randomization log with group assignment, subject name, and medical record number
  - a. Daily dosing group will take ferrous sulfate 325 mg (65 mg elemental iron) by mouth daily
  - b. Alternate day dosing group will take ferrous sulfate 650 mg (130 mg elemental iron) by mouth every other day
- 5. Prescriptions for the appropriate regimen will be provided by the research staff
  - a. If the research staff is a physician, the appropriate prescription will be sent at time of encounter
  - b. If the research staff is a non-physician, a physician research staff member will be alerted and the appropriate prescription will be sent on the same day
- 6. After patient is consented and enrolled, the provider will be notified and a note will be placed in the electronic chart indicating that the patient is enrolled in the study.

- 7. Subjects will continue to receive standard, routine prenatal care and surveillance of iron deficiency anemia in pregnancy
  - a. Research staff and PI will monitor surveillance data by chart review
- 8. 2-4 weeks after initiation of respective iron regimen research staff will contact subjects by phone to administer a 5-10 min survey to assess GI side effects and compliance with regimen.
- 9. Research staff will conduct chart review to obtain the datapoints for the primary and secondary outcomes (described in section 1)

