### 9. Recruitment Methods and Consenting Process:

Patients receiving prenatal care at the UTMB/RMCHP clinics will be screened to identify patients with a hemoglobin below 11 g/dl in the first trimester and/or 10.5 g/dl in the second trimester who also satisfy inclusion and exclusion criteria. RMCHP clinical providers will be educated about the trial prior to enrollment. We plan to identify these patients by screening the charts of patients scheduled in clinic to identify potential subjects. Information to be reviewed as part of the screening process will be hemoglobin laboratory data and relevant exclusion and inclusion history. Research staff will function as the screeners and will alert providers that their patient is a potential subject. The provider caring for that patient will then be informed of the patient's eligibility. Research staff will work with the provider to ensure that the study intervention is appropriate therapy for the patient. If the provider agrees that the study intervention is appropriate, the provider will introduce the research staff to the patient who will then explain the study the patient as part of the consenting process. A screening log will be used to track all subjects approached for the study. At the time of consent and randomization, the patient will be educated as to the dosing regimen as well as the routine treatment surveillance that will occur. This will be done by the research staff consenting the patient.

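### The only assignment method described is a log handled within the recruiting team's own sequence of steps, and nothing in the plan conceals the next assignment before enrolment

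*Combined protocol and SAP*

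**What the plan says.** The assignment mechanism is one sentence, step 4 of the procedure list under Screening in section 4: "Subjects will be randomized using a randomization log with group assignment, subject name, and medical record number".

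The surrounding text describes who acts, and when:

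- Section 4, Research Team: "All members of the research team will be able to screen and consent subjects".
- Section 4, Screening, step 2, before consent: "Research staff will confirm with provider that possible subjects are appropriate candidates for treatment with ferrous sulfate".
- Section 4, Screening, step 5a: "If the research staff is a physician, the appropriate prescription will be sent at time of encounter". Under step 5b, a non-physician alerts a physician team member, who prescribes the same day.
- Section 9: "At the time of consent and randomization, the patient will be educated as to the dosing regimen". The next sentence but one-step role is explicit: "This will be done by the research staff consenting the patient".
- Section 3 describes the study as a "comparative pragmatic open label randomized controlled trial".

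The documents do not state how the sequence is generated, whether it is blocked or stratified, who prepares or holds the log, or when an assignment becomes known. Section 14, where this might be expected, is silent. Section 12 places the master enrolment log in a password-protected database, but as a confidentiality measure. Section 11 refers to a separate submission only for monitoring.

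**The concern.** Randomization protects the comparison only if whoever decides to approach or enrol a patient cannot know which arm comes next. Here one team carries each patient from chart screening to prescription, with a case-by-case judgement of suitability before consent. If the next arm were known or guessable, that judgement, or the choice of whom to approach, could be influenced by it.

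The plan itself gives reasons to hold a view about the arms. Sections 4 and 14 expect alternate-day dosing to do well, while section 10 warns that it may leave anemia uncorrected.

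The open label does not itself cause selection bias. It does mean that the team knows past assignments, which makes a sequence with small fixed blocks partly predictable even if the list is hidden.

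At stake is the comparability of two small groups. Intention-to-treat analysis keeps the groups as they were formed; it does not correct biased formation. Section 14 plans a t test or rank-sum test for continuous outcomes, with no baseline adjustment.

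**Working it through.** No figure in the plan tests this point, so the main check is a reading of the text. The arithmetic only shows scale.

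**1. Reading the steps in order.** Suitability is confirmed (step 2), consent is sought (step 3), the patient is randomized from the log (step 4) and the prescription is sent (step 5). Section 9 puts consent and randomization in the same encounter and has the consenting staff member teach the regimen. Step 4 is in the passive voice, so use of the log by the recruiter is a strong inference and not a stated fact. No envelope, central service, electronic module or independent custodian appears anywhere.

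**2. Scale of a shift (illustration).**

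- From section 14: SD 1 g/dL (historical third-trimester hemoglobin), 39 per group, non-inferiority limit -1 g/dL, one-sided 95% confidence limit.
- Assumed: a true difference of exactly -1 g/dL, where the type I error is defined, and a shift b in the outcome favouring the alternate-day arm.
- Standard error = 1 × sqrt(2/39) = 0.2265.
- Non-inferiority is declared if the estimate exceeds -1 + 1.665 × 0.2265 = -0.623, where 1.665 is the t critical value on 76 degrees of freedom.
- False non-inferiority rate = 1 - Φ(1.665 - b/0.2265).

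| Assumed shift b (g/dL) | b/SE | False non-inferiority rate |
|---|---|---|
| 0 | 0 | 0.048 |
| 0.1 | 0.442 | 0.111 |
| 0.2 | 0.883 | 0.217 |

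With the normal critical value 1.645, the rates are 0.050, 0.114 and 0.223. The two-sided 0.05 superiority test, under no true difference, would have type I error 0.073 at b = 0.1 and 0.143 at b = 0.2.

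**3. Sensitivity to the SD.** The 39 per group reaches 90% power for 1 g/dL at SD = sqrt(39/2)/(1.960 + 1.282) = 1.36. With that SD and the critical value 1.645, the false non-inferiority rates are 0.093 and 0.160.

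**4. How many patients make such a shift.** Suppose two patients whose expected third-trimester hemoglobin differs by 1 g/dL swap arms. Each arm mean moves by 1/39 in opposite directions, so the difference moves by 2/39 = 0.051. Two swaps give about 0.10 and four give about 0.21. If steering only replaces patients within one arm, four replacements give 4/39 = 0.10 and eight give 8/39 = 0.21.

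**5. Guessing from past assignments (assumes fixed blocks, which the plan does not mention).** Staff who always guess the lagging arm, and guess at random when the arms are level, would be right 75%, 71%, 68% or 67% of the time with block size 2, 4, 6 or 8.

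**The case against.** The strongest reply is that the plan is silent, not wrong. A reader might infer that the log is an open, pre-filled list on which the recruiter reads the next arm. The documents do not say so. Names and record numbers can be entered only once a patient is identified, so the log could be a record completed at each assignment. That objection stands: foresight is not shown.

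A reader might also infer that treating providers could steer patients. Nothing gives them access to the log, and step 6 notifies them after enrolment. At most they could learn past assignments.

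The plan has some helpful features. Consent is sought before randomization, the suitability question concerns ferrous sulfate, which both arms take, and section 9 requires a log of everyone approached. These limit or help to audit selective approach. None of them hides the next assignment.

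The size of the shift is open to challenge too. The 0.1 to 0.2 g/dL comes from no document. Eligibility restricts the baseline hemoglobin range, and a baseline imbalance carries over to the outcome only in part when the two are imperfectly correlated. If the outcome is analysed as a change, as sections 1 and 4 name it, the direction of bias from a baseline imbalance is not fixed. Baseline hemoglobin is measured at screening and could be adjusted for, leaving only selection on unmeasured factors. All of this is fair, but section 14 plans no such adjustment.

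**Conclusion.** The point holds as a gap in the stated mechanism. A new team member following section 4 as written would meet no safeguard against foreseeing an assignment. Bias from this source can therefore enter, and the planned unadjusted tests would not correct it.

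The rise to 11%-22% is hypothetical. It depends on the assumed shift, SD 1, 39 evaluable patients per arm and a true difference at the margin. It must not be read as an estimate of bias in this trial. The conclusion about the missing safeguard does not depend on these figures.

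The change should be made before enrolment, because concealment cannot be added afterwards. Confidence is medium, because the log may in practice be operated more safely than the text says.

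**What to change.** Replace step 4 of the Screening procedure with text to this effect:

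- Eligibility and signed consent are recorded first, and only then is the assignment released.
- The sequence is computer-generated, and is prepared and held by someone who does not recruit.
- Release is through sequentially numbered, sealed, opaque envelopes or through an electronic module.
- If blocks are used, their sizes vary and are not disclosed to recruiters. Concealed simple randomization would also serve.
- The randomization log is kept only as a record of assignments already made.

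The cost is small: preparing the sequence, and managing envelopes or system access across clinics served by travelling staff. It needs no extra visits or blood draws and does not alter either regimen.

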#### Additional details

The routine prenatal visits for pregnant patients with anemia include at least monthly venipunctures to monitor the treatment of anemia and intervene if necessary. Our primary outcome of 3rd trimester hemoglobin as well as laboratory secondary outcomes are convenient data points collected in the standard treatment and surveillance of anemia in pregnancy. As such patients will not need any study specific venipuncture or visits. Prenatal visits are frequent with monthly visits in the 1st trimester, bi-monthly visits in the 2nd trimester, and weekly visits in the 3rd trimester with 24 hour after hours care phone services available. The frequency and ready availability of appointments ensures that any symptomatic patient will quickly be seen and evaluated.

Any subject that requires escalation of treatment beyond oral supplementation (IV iron infusion or blood transfusion) will be referred to receive appropriate intervention. These subjects will still be included in the intent-to-treat analysis. The routine surveillance of anemic pregnant patients described above ensures that any treatment failure will be quickly identified and addressed.

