### 6. Criteria for Inclusion of Subjects:

- Maternal age  $\geq$  18 years and <50 years
- Prenatal care provided at UTMB
- Hemoglobin below 11 g/dl in the first trimester and/or 10.5 g/dl in the second trimester
- Microcytic anemia
- Singleton gestation

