### 8. Sources of Research Material:

The primary and secondary outcomes for this trial will be obtained from chart review for enrolled patients.

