## 14. Biostatistics:

We hypothesize that the intervention group will have a higher hemoglobin level in the third trimester than the standard group. The primary analysis will be conducted on an intention-to- treat basis. Between-group differences in continuous variables, will be assessed using Student t test or Man-Whitney rank sum test and results will be given as mean, standard deviation or median range as appropriate. Categorical variables will be assessed using the Pearson chi-square test or Fisher exact test as appropriate. For dichotomous endpoints, relative risk (RR) and 95% CI values will be calculated. P <0.05 will be considered significant. The analysis will be performed after study completion.

Based on our historical data at our center of 56 anemic women with iron deficient anemia that received standard daily iron supplementation: third trimester hemoglobin mean of  $10.27 \pm 1$  g/dL. We will first do a noninferiority approach. If noninferiority is not met, we will do a superiority analysis. For the noninferiority: If there is truly no difference between the standard and experimental treatment, then 68 subjects will be required to be 90% sure that the lower limit of a one-sided 95% confidence interval (or equivalently a 90% two-sided confidence interval) will be above the non-inferiority limit of -1. For the superiority: We estimate that a minimum sample of 39 per group, total N= 78 women will be needed to provide a power of 90% with a two-sided alpha level of 0.05 and a 1 g/dL difference in hemoglobin between control and intervention. We plan to enroll 86 patients in order to account for up to 10% missing data or loss to follow up. If no differences are noted among groups (non inferiority hypothesis failed) we will be performing a superiority approach. Stata 16 will be used for the statistical analysis.

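### Compliance is self-reported once, 2-4 weeks after starting iron; later adherence is unmeasured and no hemoglobin analysis uses compliance, although non-inferiority is tested first by intention to treat

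*Combined protocol and SAP*

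**What the plan says.** Section 3 announces the survey: "Each group will receive a phone survey 2-4 weeks after initiation of therapy to assess side effects of each group as well as compliance". Section 4 (Screening, step 8) repeats it: "2-4 weeks after initiation of respective iron regimen research staff will contact subjects by phone". Section 4 (Survey Details) describes the same call and continues: "Study subjects will then resume standard prenatal care visits". No second call, pill count, diary or refill check is described anywhere.

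Section 8 gives the source of all outcomes: "The primary and secondary outcomes for this trial will be obtained from chart review for enrolled patients". The outcome lists in section 1 include parenteral iron and peripartum transfusion. They do not include compliance, refills or other oral iron.

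Treatment may start at very different times before the outcome. Entry is by "Hemoglobin below 11 g/dl in the first trimester and/or 10.5 g/dl in the second trimester" (section 6). The outcome sample comes from routine care and has no fixed week: "Our primary outcome of 3rd trimester hemoglobin as well as laboratory secondary outcomes are convenient data points" (section 4, Additional details).

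On analysis, section 14 says: "The primary analysis will be conducted on an intention-to- treat basis". Non-inferiority is tested first, and the lower confidence limit "will be above the non-inferiority limit of -1" is the criterion. No per-protocol or other adherence-based analysis is mentioned.

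**The concern.** Both arms receive the same product at the same average amount: 65 mg elemental iron daily, against 130 mg every other day, which is 130 / 2 = 65 mg per day. Schedule is therefore the whole contrast, and a woman who moves to the other schedule, or stops, removes it for herself. The trial is open label, and section 1 says that many iron products are prescribed at the provider's discretion, so such changes are possible.

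In a superiority test, drift of this kind costs power. In a non-inferiority test analyzed by intention to treat, it pulls the means together and makes the favorable conclusion easier to reach. The planned data could not show whether similar hemoglobin values mean that the two schedules work equally well or that both arms ended up doing much the same thing. Adherence that was not recorded during treatment cannot be reliably recovered after delivery.

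**Working it through.** **1. How much of treatment the call covers.** The protocol gives no figure for this, so there is none to reproduce. Inputs: call at c = 2 to 4 weeks after start (sections 3 and 4). Assumptions: outcome sample at gestational week D = 28 to 40, and start at week S = 12, 20 or 24. None of these weeks is in the documents.

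Uncovered weeks = D − S − c. Uncovered share = (D − S − c) / (D − S). The smallest value uses D = 28 and c = 4; the largest uses D = 40 and c = 2.

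| Start | Treatment to sample | Smallest gap | Largest gap | Uncovered share |
|---|---|---|---|---|
| Week 12 | 16-28 weeks | 12 of 16 | 26 of 28 | 75-93% |
| Week 20 | 8-20 weeks | 4 of 8 | 18 of 20 | 50-90% |
| Week 24 | 4-16 weeks | 0 of 4 | 14 of 16 | 0-88% |

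**2. Which standard deviation to use.** Section 14 states an SD of 1 g/dL, a margin of 1, 90% power and totals of 68 (non-inferiority) and 78 (superiority). With SD 1:

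- Non-inferiority, one-sided 5%: 2 × (1.645 + 1.282)² = 17.1, so 18 per arm, 36 in total.
- Superiority, two-sided 5%: 2 × (1.960 + 1.282)² = 21.02, so 22 per arm, 44 in total.

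The stated totals do not follow from SD 1. Solved backwards they imply an SD of about 1.41 (for 68) and 1.36 (for 78). That is a separate matter; here it is the reason to show both SD 1 and SD 1.4.

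**3. What drift does to the non-inferiority test (illustration).** Suppose alternate-day dosing is truly 1 g/dL worse when both regimens are followed, exactly at the margin, and that drift shrinks the deficit to d. With 39 per arm:

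P(declare non-inferiority) = Φ[(1 − d) / (SD × √(2/39)) − 1.645]

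For d = 0.7 and SD 1: √(2/39) = 0.2265; 0.3 / 0.2265 = 1.325; 1.325 − 1.645 = −0.320; Φ(−0.320) = 37%.

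| Remaining deficit d (g/dL) | SD 1 | SD 1.4 |
|---|---|---|
| 1.0 | 5% | 5% |
| 0.9 | 11% | 9% |
| 0.8 | 22% | 16% |
| 0.7 | 37% | 24% |
| 0.5 | 71% | 47% |

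The amounts of dilution are assumed; the documents give no adherence rate. Given drift that makes the arms more alike, the direction does not depend on them.

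**The case against.** The strongest defense is that section 3 calls the trial pragmatic and section 14 makes intention-to-treat primary. The effect of being assigned to a schedule, real-life adherence included, can be estimated without adherence data. This stands: the primary analysis is valid for that question, and the false-declaration rates above refer to the effect under adherence, not to the effect of assignment. It does not remove the difficulty of interpreting a non-inferiority result, and the protocol itself motivates the trial by absorption physiology.

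A reader might infer that exposure is never measured. The documents do not support that. The call records the first weeks in both arms, and for a late second-trimester start it can cover most or all of the interval. Women are approached only at the appointment after their screening visit, which pushes some starts later.

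A reader might also infer that any added iron goes unseen. Parenteral iron and transfusion are listed secondary outcomes, escalated subjects stay in the intention-to-treat analysis, and staff follow surveillance data by chart review (Screening, step 7). The gap is limited to tablets stopped, schedules switched and other oral iron.

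Finally, a treatment period of up to six months is an upper-end inference, not a stated duration, and nothing in the documents shows that adherence is best in the first weeks. Neither is relied on here.

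One further objection is right: a second call alone would change no reported result. It needs an analysis that uses it.

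**Conclusion.** The point holds as a gap in measurement and analysis, not as an error in the primary analysis. Compliance is self-reported once, early; adherence, schedule switching and other oral iron after that call are not measured. The generic tests in section 14 could compare survey answers between arms, but no analysis of hemoglobin takes compliance into account.

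On the assumed gestational weeks, at least half of treatment is uncovered for starts at week 12 or week 20; for a week-24 start the share runs from none to 88%. How far this would affect the conclusion cannot be fixed from the documents, because the amount of drift is unknown. At 39 per arm, a remaining deficit of 0.7 g/dL out of a true 1 g/dL would raise the chance of declaring non-inferiority from 5% to 24-37%. The change is worth making before enrollment because it is cheap and can only be made prospectively.

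**What to change.** 1. **Section 4, Screening, step 8:** repeat the same compliance and GI call once, in both arms, in a fixed third-trimester window. Ask about the period since the first call: regimen actually taken, doses per week, date stopped, and any other oral iron. The outcome sample has no fixed week, so define the call window by gestational age and align it with the outcome week once that is set.
2. **Chart-review data list:** add refill dates of the study prescription where the chart holds them. The protocol says only that prescriptions are sent, so availability needs checking.
3. **Section 14:** add an adherence-based (per-protocol) sensitivity analysis of the non-inferiority comparison, with adherence defined before the data are seen. Keep intention-to-treat as primary and report the two side by side. The per-protocol set is selected after randomization, so it supports the primary result and does not replace it.
4. **While editing:** reconcile the timing of the first call (from initiation in section 3 and step 8, from randomization in Survey Details) and its length (10-15 minutes in section 3, 5-10 minutes in section 4).

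**Cost:** 86 × 5 / 60 = 7.2 hours to 86 × 15 / 60 = 21.5 hours of existing staff time, before any time for the added questions, plus one chart field and one analysis. No study visit or blood draw is added. Some calls will be missed, self-report will carry error, and asking about adherence near the outcome may influence behavior and makes the design slightly less pragmatic.
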